### 16.2. DEATHS

If any subjects die during the trial as recorded on the “End of trial visit” page of the eCRF, the information will be presented in a summary table and a data listing based on the RND set.

### 16.3. LABORATORY EVALUATIONS

Results from the central laboratory will be included in the reporting of this trial for Serum chemistry, Hematology, and Urinalysis. A list of laboratory assessments performed at screening, admission (Day -1), Day 10, Day 22 and Day 57 is included in section 5.2.3 of protocol.

Presentations will use SI Units.

Quantitative laboratory measurements reported as “< X”, i.e. below the lower limit of quantification (BLQ), or “> X”, i.e. above the upper limit of quantification (ULQ), will be converted to X for the purpose of quantitative summaries, but will be presented as recorded, i.e. as “< X” or “> X” in the listings.

Qualitative laboratory urinalysis results measured by central laboratory will be classified to the categories “Positive” and “Negative” based on the central laboratory normal reference.

The handling of retests, unscheduled and end of trial measurements is described in Section 7.6. However, laboratory values taken after the first and single dose of trial medication up to a period of 10 weeks after the last dose of the trial medication will be assigned to the treatment phase for evaluation. All available data (including IGRA results) will be listed.

The following summaries will be provided for laboratory data:

- Actual and change from baseline by visit (for quantitative measurements)
- Shift from baseline category (Low / Normal / High) by visit (all parameters except urinalysis parameters)
- Shift from baseline category (Negative / Positive) by visit (for urinalysis parameters)
- Incidence of possible Hy's law subjects
- Incidence of possible DILI
- The time course of ALT, AST and total bilirubin (TBL) for all possible Hy's law subjects, all parameters shown on a logarithm to base 10 scale of the multiple of the upper limit of normal (ULN) (Y axis) versus days since treatment start (X axis)

- Scatter plots for Evaluation of Potentially Drug-Induced Liver Injury:
  - log ALT on the X axis and log TBL on the Y axis, both shown on a logarithm to base 10 scale of the multiple of the ULN
  - log AST on the X axis and log TBL on the Y axis, both shown on a logarithm to base 10 scale of the multiple of the ULN

#### 16.3.1. LABORATORY SPECIFIC DERIVATIONS

- Log ALT = logarithm to base 10 scale of the multiple of the ULN of ALT
- Log AST = logarithm to base 10 scale of the multiple of the ULN of AST
- Log TBL = logarithm to base 10 scale of the multiple of the ULN of TBL
- Potential Hy's law categories:
  - Category 1: ALT or AST  $\geq 3 \times \text{ULN}$  and TBL  $\geq 2 \times \text{ULN}$  within the same sample
  - Category 2: TBL  $\geq 2 \times \text{ULN}$  within 30 days after transaminase peak (ALT or AST  $\geq 3 \times \text{ULN}$ )

Potential Hy's Law subjects are defined as subjects with laboratory data in at least one Potential Hy's law categories at any time point of the trial.

- Drug induced liver injury (DILI):
  - Category 1 : AST and/or ALT  $\geq 3$  times ULN and TBL  $\geq 2$  times ULN within the same sample
  - Category 2 : marked peak aminotransferase (ALT, and/or AST) elevations  $\geq 10$  fold ULN

#### 16.3.2. LABORATORY REFERENCE RANGES AND MARKEDLY ABNORMAL CRITERIA

Quantitative laboratory measurements will be compared with the relevant laboratory reference ranges in SI units and categorized as:

- Low: Below the lower limit of the laboratory reference range.
- Normal: Within the laboratory reference range (upper and lower limit included).
- High: Above the upper limit of the laboratory reference range.

#### 16.3.3. OTHER SAFETY LABORATORY EVALUATIONS

##### 16.3.3.1 Pregnancy test

Descriptive table will present pregnancy results for females overall on SAF.

The pregnancy results will be listed as well on ENR.

Document: BI\_1297-0015\_SAP\_Final\_v1.0  
Author: [REDACTED]

Version Number: Final 1.0  
Version Date: 30Sep2022

Template No: CS\_TP\_BS016 – Revision 7  
Effective Date: 01Nov2021

Reference: CS\_WI\_BS005

## 16.4. ECG EVALUATIONS

Results from the central ECG (Electrocardiogram) will be summarized by visit to the categories as recorded in the eCRF page "12-Lead-ECG" ("normal", "abnormal, not clinically significant" and "abnormal, clinically significant").

In case of multiple assessments at the same date, the evaluation with the worst result is taken into account.

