5.2.4 Electrocardiogram

Twelve-lead ECGs (I, II, III, aVR, aVL, aVF, V1 - V6) will be recorded using a computerised electrocardiograph (i.e. Burdick ELI 150C) at the times provided in the [Flow Chart](#).

To achieve a stable heart rate at rest and to assure high quality recordings, the site personnel will be instructed to assure a relaxed and quiet environment, so that all subjects are at complete rest.

Proprietary confidential information © 2021 Boehringer Ingelheim International GmbH or one or more of its affiliated companies

All ECGs will be recorded for a 10 sec duration after subjects have rested for at least 5 min in a supine position. ECG assessment will always precede all other trial procedures scheduled for the same time to avoid compromising ECG quality.

All ECGs will be stored electronically. Electrode placement will be performed according to the method of Wilson, Goldberger and Einthoven modified by Mason and Likar (hips and shoulders instead of ankles and wrists). Precise electrode placement will be marked with an indelible mark on the skin to allow reproducible placement throughout the trial.

All locally printed ECGs will be evaluated by the investigator or a designee. Abnormal findings will be reported as AEs (during the trial) or baseline conditions (if identified at the screening visit) if assessed to be clinically relevant by the investigator. Any ECG abnormalities will be carefully monitored and, if necessary, the subject will be removed from the trial and will receive the appropriate medical treatment.

ECGs may be repeated for quality reasons (for instance, due to alternating current artefacts, muscle movements, or electrode dislocation) and the repeated ECG will be used for analysis. Additional (unscheduled) ECGs may be collected by the investigator for safety reasons.

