### 4.3. CHANGES TO ANALYSIS FROM PROTOCOL

There are no changes in the analysis plans relative to the study protocol.

---

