## 7.6. RETESTS, UNSCHEDULED VISITS AND EARLY TERMINATION DATA

In general, for by-visit summaries, data recorded at the nominal visit will be presented. In the case of a retest, an unscheduled assessment will be created.

Unscheduled measurements (unless assigned to a planned visit number, as stated above) will not be included in by-visit summaries.

Early treatment termination data will not be included in by-visit table summaries and by-visit graphs.

Listings will include scheduled, unscheduled, retest and early discontinuation data collected in the electronic Case Report Form (e-CRF) database.

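### SAP 16.4 takes the worst same-date ECG with no exception for quality repeats, although protocol 5.2.4 says the repeat is analysed, and SAP 4.3 declares no change

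*SAP*

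**What the plan says.** Protocol 5.2.4 covers two kinds of extra ECG. The first is a repeat made because the recording was technically poor, for example through electrical interference, movement or a displaced electrode. For this kind it states the consequence: "and the repeated ECG will be used for analysis". The second kind is dealt with in its own sentence: "Additional (unscheduled) ECGs may be collected by the investigator for safety reasons". The same section also says "All locally printed ECGs will be evaluated by the investigator or a designee".

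SAP 16.4 summarises ECGs by visit in three ordered categories taken from the eCRF page: normal, abnormal without clinical significance, and abnormal with clinical significance. Its rule for several ECGs on one day is: "In case of multiple assessments at the same date, the evaluation with the worst result is taken into account". It does not separate quality repeats from safety ECGs.

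SAP 7.6 contains a general rule: "In the case of a retest, an unscheduled assessment will be created". Unscheduled measurements stay out of by-visit summaries unless they are assigned to a planned visit.

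SAP 4.3 states: "There are no changes in the analysis plans relative to the study protocol".

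**The concern.** For one and the same event, a same-day repeat after a poor recording, the protocol selects the repeat and the SAP selects whichever evaluation is worse. A worst-result convention is sensible when several valid ECGs exist. It is not sensible for a tracing that the protocol says has been superseded because of a recording fault.

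Wherever SAP 16.4 and the protocol disagree, the SAP gives the more abnormal category, so the error runs in one direction. The table could also fail to match the adverse event data. Protocol 5.2.4 turns clinically relevant abnormal findings during the trial into adverse events. An artefact tabulated in the most severe category might have no matching event.

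Because SAP 4.3 declares no change, a reader of the report would assume that the protocol rule had been followed.

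**Working it through.** No sample size, power or error-rate figure bears on this point, and the plan gives no figure to reproduce. The check compares the texts and counts outcomes under each rule.

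**Inputs**
- Three ordered categories (SAP 16.4), coded here as 0 = normal, 1 = abnormal, not clinically significant, 2 = abnormal, clinically significant.
- Protocol rule after a quality repeat (protocol 5.2.4): result = repeat.
- SAP 16.4 rule: result = max(first, repeat).
- SAP 7.6 rule, if it were applied and the repeat were not assigned to the planned visit: result = first.

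**All 3 × 3 = 9 pairs**

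| First | Repeat | Protocol 5.2.4 | SAP 16.4 | SAP 7.6, if applied |
|---|---|---|---|---|
| 0 | 0 | 0 | 0 | 0 |
| 0 | 1 | 1 | 1 | 0 (differs) |
| 0 | 2 | 2 | 2 | 0 (differs) |
| 1 | 0 | 0 | 1 (differs) | 1 (differs) |
| 1 | 1 | 1 | 1 | 1 |
| 1 | 2 | 2 | 2 | 1 (differs) |
| 2 | 0 | 0 | 2 (differs) | 2 (differs) |
| 2 | 1 | 1 | 2 (differs) | 2 (differs) |
| 2 | 2 | 2 | 2 | 2 |

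SAP 16.4 departs from the protocol in 3 of 9 pairs, exactly those in which the first tracing is rated worse than the repeat. The two agree in the other 9 − 3 = 6. SAP 7.6, if it governed ECGs, would depart in 6 of 9, so it does not restore the protocol rule. These are counts of possible pairs and not probabilities.

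**Can a differing pair arise?** Two conditions are needed: the defective tracing is entered in the eCRF with an evaluation, and that evaluation is worse than the repeat's. Protocol 5.2.4 has every locally printed ECG evaluated, so a poor first tracing can carry a category. The documents do not say whether a rejected tracing is entered alongside its replacement. If a site enters only the repeat, no error arises.

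**Which SAP rule governs?** SAP 16.3 (laboratory) and 16.5 (vital signs) refer retests to SAP 7.6. SAP 16.4 does not, and it sets its own same-date rule. SAP 7.6 is also framed as a general rule with an exception for measurements assigned to a planned visit. The operative conflict is therefore between protocol 5.2.4 and SAP 16.4.

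**The case against.** The best defence is that the two texts can be read together. SAP 1 assumes that its reader knows the protocol. On that view protocol 5.2.4 first decides which tracing is valid, and SAP 16.4 then handles several valid evaluations, such as an added safety ECG. This would be a sensible plan, but SAP 16.4 does not say it. Its rule covers any multiple assessments on one date, and a programmer working from that section would apply it to all of them.

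The defence is right about the consequences, which are small:
- The by-visit category table is an SAP addition. The ECG reporting that protocol 7.2.5 describes is of relevant findings as adverse events, and its safety analyses are descriptive, without hypothesis testing.
- Nothing suggests that recording faults differ between arms, and the investigators are blinded. The expected effect is some excess of abnormal readings overall, not a bias between formulations.
- Misclassification is conditional on what the site enters.

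A reader might also infer that a faulty Day -1 tracing becomes the baseline and hides a later true change. The documents do not support this. SAP 7.5 takes the last non-missing pre-dose measurement, unscheduled ones included, so a repeat made after a faulty tracing would be the baseline. SAP 16.4 also plans no ECG change or shift from baseline, whereas SAP 16.3 plans both for laboratory data and SAP 16.5 plans change for vital signs.

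**Conclusion.** The contradiction is real and undeclared. SAP 16.4 as written is a wrong rule for quality repeats, not merely an incomplete one, and for this item the statement in SAP 4.3 is incorrect.

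The effect is limited to the descriptive by-visit ECG table, and there only to repeats whose superseded tracing was entered with a worse category. The primary pharmacokinetic analysis does not depend on it.

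The number of affected readings cannot be estimated from the documents. A reader might be tempted to put a figure on it: about six ECG occasions in the Flow Chart × 200 subjects = 1,200 tracings, of which 2% to 5% repeated would be 24 to 60. That repeat rate is purely an assumption. The result counts all repeats, so even if the rate were right it would be only an upper bound on the misclassified readings. Nor do the documents show that artefact readings will in fact be tabulated; they show that the rule allows it.

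**What to change.** Change SAP 16.4 to: *If an ECG is repeated for quality reasons, the repeat replaces the original at that visit (protocol 5.2.4); the worst-result rule applies only to other same-date ECGs.* Add that, for ECGs, this takes precedence over the general retest rule in SAP 7.6.

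Alternatively, keep the worst-result rule throughout and declare and justify the departure in SAP 4.3. Either choice should be settled before unblinding.

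The cost is one or two sentences and one selection rule in the ECG program. The first option also needs the data to support it: either the eCRF identifies a quality repeat, or sites do not enter the superseded tracing as an evaluable result. The documents do not show whether such a field exists. If it does not, an entry instruction to the sites is needed as well.

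A minor alignment can go into the same edit. SAP 16.4 describes its source as central ECG results, while it takes the categories from the eCRF and protocol 5.2.4 describes local evaluation by the investigator or a designee. The wording should name the investigator's evaluation recorded in the eCRF.

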## 16.5. VITAL SIGNS

The following Vital Signs measurements will be reported for this study:

- Systolic and Diastolic Blood Pressure (mmHg)
- Pulse Rate (bpm)
- Temperature (°C)
- Weight (kg)

The handling of retests, unscheduled and end of trial measurements is described in Section 7.6.

The summary of actual and change from baseline by visit will be provided for vital sign data.

## 16.6. PHYSICAL EXAMINATION

Physical examination findings are required to be reported as relevant medical history/baseline condition or as adverse event. No separate listing or analysis of physical examination findings will be prepared.

## 16.7. OTHER SAFETY ASSESSMENTS

[REDACTED]

[REDACTED]

[REDACTED]

[REDACTED]

[REDACTED]

[REDACTED]

[REDACTED]

A horizontal bar chart with 10 categories on the y-axis and 1000 samples on the x-axis. The categories are represented by black bars. Category 0 has the longest bar, followed by categories 1, 2, 3, 4, 5, 6, 7, 8, and 9, which all have equal lengths.

Category	Number of Samples
0	1000
1	100
2	100
3	100
4	100
5	100
6	100
7	100
8	100
9	100

### 16.7.2. LOCAL TOLERABILITY

Outputs for local tolerability will be based on the SAF.

The number and percentage of subjects with injection site reactions (assessed at Day 1 from the time of the injection until Day 2, prior to discharge from the trial site) will be summarized by treatment for each injection site reaction.

The number of patients with at least one injection site reaction post-administration will also be reported.

All injection site reactions will be listed.

Document: BI\_1297-0015\_SAP\_Final\_v1.0  
Author: [REDACTED]

Version Number: Final 1.0  
Version Date: 30Sep2022

Template No: CS\_TP\_BS016 – Revision 7  
Effective Date: 01Nov2021

Reference: CS WI BS005

Copyright © 2009, 2010, 2012, 2016, 2018, 2019, 2021 [REDACTED]. All Rights Reserved. The contents of this document are confidential and proprietary to [REDACTED] Holdings Inc. and its subsidiaries. Unauthorized use, disclosure or reproduction is strictly prohibited.

## 17. PHARMACOKINETIC DATA

All outputs for pharmacokinetic outcomes will be based on the PKS. BI 695501 plasma concentrations and PK parameters will be listed with descriptive statistics. Individual plasma concentrations, as well as (geometric) mean plasma concentrations will be plotted versus time (linear and semi-log scale). Individual and gMean PK parameters for test and reference treatment will also be part of the figures. Boxplots with whiskers will be displayed for the primary endpoints.

PK analysis constitutes the primary objective of this trial to compare two formulations of BI 695501 administration [40 mg / 0.4 mL (T) vs 40 mg / 0.8 mL (R)].

[figure not shown]
### 17.1. PRIMARY PHARMACOKINETIC ANALYSIS

#### 17.1.1. PHARMACOKINETIC VARIABLES & DERIVATIONS

The primary endpoints are:

- AUC0-1344 (area under the concentration-time curve of the analyte in plasma over the time interval from 0 to 1344 hours after dose)
- AUC0-∞ (area under the concentration-time curve of the analyte in plasma over the time interval from 0 extrapolated to infinity) based on observed concentration at time of last measurable concentration
- Cmax (maximum measured concentration of the analyte in plasma)

No secondary endpoints for PK are defined.

### 17.1.2. MISSING DATA METHODS FOR PRIMARY PHARMACOKINETIC VARIABLES

Handling of missing PK data will be performed according to the relevant SOP of the Sponsor.

For the non-compartmental analysis, concentration data identified with NOS (no available sample), NOR (no valid result) or NOA (not analyzed) will generally not be considered. Concentration values in the lag phase identified as BLQ will be set to zero. All other BLQ values of the profile will be ignored. The lag phase is defined as the period between time zero and the first time point with a concentration above the quantification limit.

Descriptive statistics of parameters and concentrations are calculated only when a parameter value is available for at least 2/3 of the treated individuals. If the actual sampling time is not recorded or is missing for a certain time point, the planned time will generally be used for this time point instead. PK parameters that cannot be determined will be identified as "not calculated".

### 17.1.3. ANALYSIS OF PHARMACOKINETIC VARIABLES

The PK parameters will be calculated according to the BI SOP 'Standards and processes for analyses performed within Clinical Pharmacokinetics/ Pharmacodynamics' [according to the relevant SOP of the Sponsor].

Only concentration values within the validated concentration range and actual sampling times will be used for the calculation of PK parameters. Concentrations used in the PK calculations will be in the same format as provided in the bioanalytical report (that is, to the same number of decimal places provided in the bioanalytical report).

If a pre-dose concentration value is greater than 5% of Cmax, the subject's PK data will not be included in any statistical evaluations, in accordance with international guidance. The individual PK parameters of such a subject will be calculated and listed separately. These PK parameters and observed concentrations will not be included in descriptive statistics. If a pre-dose concentration is above the limit of quantification (BLQ), but less than or equal to 5% of the subject's Cmax value, the subject's data, without any adjustments, will be included in all PK measurements and calculations.

The primary PK endpoints will be plotted using boxplots with whiskers for PK parameters after administration of test product (40 mg BI 695501 100 mg/ml, 0.4 ml) and administration of the reference product (40 mg BI 695501 50 mg/ml, 0.8 ml).

Descriptive statistics of plasma concentrations and PK endpoints, as well as the tables and graphs for the pharmacokinetic noncompartmental analyses, will follow specific definitions of this SAP or, otherwise, the BI standard procedure "Standards and processes for analyses performed within Clinical Pharmacokinetics/Pharmacodynamics" according to the SOP of the sponsor.

### 17.1.4. PRIMARY ANALYSIS FOR PHARMACOKINETIC VARIABLES

Relative bioavailability of 40 mg/ 0.4 ml BI 695501 formulation (Test, T) compared to 40 mg/ 0.8 ml of

Document:	BI_1297-0015_SAP_Final_v1.0	Version Number:	Final 1.0
Author:	[REDACTED]	Version Date:	30Sep2022

Template No: CS\_TP\_BS016 – Revision 7

Reference: CS\_WI\_BS005

Effective Date: 01Nov2021

Copyright © 2009, 2010, 2012, 2016, 2018, 2019, 2021 [REDACTED]. All Rights Reserved. The contents of this document are confidential and proprietary to [REDACTED] Holdings Inc. and its subsidiaries. Unauthorized use, disclosure or reproduction is strictly prohibited.

BI 695501 formulation (Reference, R) will be estimated by the ratios of the geometric means (T/R) for the primary endpoints. Additionally, their two-sided 90% confidence intervals (CIs) will be provided.

The primary PK endpoints for BI 695501 will be estimated using an analysis of covariance (ANCOVA) model on the logarithmic scale (natural logarithm) with effects for treatment, location of trial medication injection and baseline body weight (continuous).

The ANCOVA model is described by the following equation:

$y_{kjm} = \mu + \tau_k + \varphi_j + \beta * \text{weight}_{km} + e_{kjm}$ , where

$y_{kjm}$  = logarithm of PK parameter measured on subject m receiving treatment k at location j,

$\mu$  = the overall mean,

$\tau_k$  = the k-th treatment effect, k = 1, 2 (1=T (BI 0.4 mL), 2=R (BI 0.8 mL)),

$\varphi_j$  = the jth effect of location (thigh, abdomen), j= 1, 2,

$\beta$  = the slope parameter for the baseline body weight covariate,

$\text{weight}_{km}$  = baseline body weight of subject m receiving treatment k, and,

$e_{kjm}$  = the random error associated with the m-th subject who received in location j treatment k,

where  $e_{kjm} \sim N(0, \sigma_k^2)$  are independent random variables.

The following SAS code will be used:

(M1) 

```
PROC MIXED data= ADPP<restricted to parameter> METHOD=REML;
  CLASS TRTP (ref="R") Location;
  MODEL AVAL = TRTP Location BASE_WEIGHT /DDFM=KR;
  LSMEANS TRTP;
  ESTIMATE 'BI 695501 T versus R' TRTP 1 -1 /alpha=0.1;
RUN;
```

For model (M1), AVAL refers to the PK endpoint value on the logarithmic scale.

For each PK endpoint, (M1) estimates the difference between the means for log(T)-log(R) by the difference in the corresponding adjusted means (least-squares means), and a two-sided 90% CI based on the t-distribution will be computed.

These quantities will then be back-transformed to the original scale to provide the point estimate and 90% CIs for the corresponding ratio of geometric means (T/R) for each PK endpoint.

A forest plot will be produced to report the results of the primary analysis.

---

Document: BI\_1297-0015\_SAP\_Final\_v1.0  
Author: [REDACTED]

Version Number: Final 1.0  
Version Date: 30Sep2022

Template No: CS\_TP\_BS016 – Revision 7  
Effective Date: 01Nov2021

Reference: CS\_WI\_BS005

---

